### 9.2.3 Local and local regional recurrence rate:

The cumulative incidence of local and local regional recurrence will be estimated using the cumulative incidence function treating death as the competing risk. In addition, local and local regional recurrence free survival will be summarized using the Kaplan-Meier estimators. The Clinical Cancer Research (CCR) database or data warehouse (as applicable) will be utilized to identify comparison group patients. The Cox proportional hazards model may be used to compare recurrence of study participants and comparison groups. Follow up time will be censored at the time of a competing event.

### 9.2.4 Economic Analysis:

Cost-effectiveness (CE) analysis of hypofractionated radiation versus standard fractionation will be explored using cost data and quality adjusted life years (QALYs) (i.e. effectiveness side). A societal perspective will be applied for the analysis because the direct costs (i.e. resource used) relevant to treatments/intervention, indirect costs (i.e. resource lost such as travel time, lost productivity) and side-effects related costs will be considered. Cost for the intervention will be measured for the cost of therapy, medications, hospitalization and medical visits. Costs for treatments due to side effects will be collected. Patient times spent for treatment, travel and lost productivity will be converted to costs using year 2022 mean adult US wage rate. Because costs related to the intervention will be occurred in different years (for example, 2018~2022), they will be adjusted to year 2022 US dollars using the medical component of the Consumer Price Index. If charged amounts relevant to the treatments are available only (i.e. plan paid amounts or reimbursed amounts are not available), they will be converted to costs by using cost-to-charge ratios. We will not compare charges or costs between institutions. The quality of life (QoL) measures will be based on the BREAST-Q and EQ-5D survey and will be used to calculate Quality Adjusted Life Years (QALYs) for the effectiveness side. Because costs and effects will be measured over multiple years, both costs and effects will be discounted at the rate of 3.5%. We will utilize the EQ-5D and Breast-Q to assist in the QALY analysis. See appendix IV. Once parameters are computed: 1) mean differences in cost and effect between treatments, 2) variances for differences in costs and effects, and 3) covariance between effectiveness and cost difference, the incremental cost-effectiveness ratio (ICER) or incremental net benefits summarizing the monetary value of the intervention will be calculated.

$$ICER = \frac{Cost_{\text{Hypofractionated Radiation}} - Cost_{\text{Standard Fractionation}}}{Effect_{\text{Hypofractionated Radiation}} - Effect_{\text{Standard Fractionation}}}$$

A CE acceptability curve will be used to quantify and graphically depict uncertainty in the analysis. To consider uncertainty in parameters, probabilistic sensitivity analysis utilizing Monte Carlo simulation (i.e. second-order simulation) will be conducted. To reflect the uncertainties in costs and in effects, a gamma distribution for costs and a normal distribution for effects will be adopted. And one-way sensitivity analyses will be conducted to consider an uncertainty of one parameter at a time over a range of 95% confidence interval in cost and effectiveness measures.

Protocol name: NOVEMBER (Novem- (9), BrEast Radiation), A Phase II trial of a 9 day course of whole breast radiotherapy for early stage breast cancer.

Version Date: 23NOV2021

Principal Investigator: [name]

## **10 REGISTRATION GUIDELINES**

**Patients must meet all of the eligibility requirements listed in Section 4 prior to registration.**

**Study related screening procedures can only begin once the patient has signed a consent form. Patients must not begin protocol treatment prior to registration.**

Treatment should start within five working days after registration.

To register eligible patients on study, complete a Clinical Trials Office Patient Registration Form and submit to: [[contact]](mailto:[contact]).

## **11 DATA SUBMISSION SCHEDULE**

The Case Report Forms (CRFs) are a set of (electronic or paper) forms for each patient that provides a record of the data generated according to the protocol. CRF's should be created prior to the study being initiated and updated (if applicable) when amendments to the protocol are IRB approved. **Data capture should be restricted to endpoints and relevant patient information required for planned manuscripts.** These forms will be completed on an on-going basis during the study. The medical records will be source of verification of the data. During the study, the CRFs will be monitored for completeness, accuracy, legibility and attention to detail by a member of the Research Compliance Office. The CRFs will be completed by the Investigator or a member of the study team as listed on the Delegation of Duties Log. The data will be reviewed no less than annually by the Data and Safety Monitoring Committee. The Investigator will allow the Data and Safety Monitoring Committee or Research Compliance Office personnel access to the patient source documents, clinical supplies dispensing and storage area, and study documentation for the above-mentioned purpose. The Investigator further agrees to assist the site visitors in their activities.

## **12 ETHICAL AND REGULATORY CONSIDERATIONS**

### **12.1 Informed consent**

Informed consent will be obtained from all research participants prior to performing any study procedures using the most recent IRB approved version. Patients who volunteer to complete the Health Care Expense Survey must be provided with the Informed Consent Letter prior to completing the questionnaire.

### **12.2 Institutional Review**

Study will be approved by the Institutional Review Board of University of Utah.

### **12.3 Data and Safety Monitoring Plan**

A Data and Safety Monitoring Committee (DSMC) is established at Huntsman Cancer Institute (HCI) and approved by the NCI to assure the well-being of patients enrolled on Investigator Initiated Trials that do not have an outside monitoring review. Roles and responsibilities of the DSMC are set forth in the NCI approved

plan. The activities of this committee include a quarterly review of adverse events including SAEs, important medical events, significant revisions or amendments to the protocol, and approval of cohort/dose escalations. If the DSMC and/or the PI have concerns about unexpected safety issues, the study will be stopped and will not be resumed until the issues are resolved. The DSMC also reviews and approves audit reports generated by the Research Compliance Office.

All **phase II** studies are reviewed by the full committee at each quarterly DSMC meeting. This includes a review of all serious adverse events (SAEs) occurring in patients treated at HCI or its affiliates as well as all grade 3 or greater toxicities for patients on treatment and within 30 day follow-up window (only if possibly, probably or definitely related).

## 12.4 Adverse Events / Serious Adverse Events

This study will utilize the CTCAE (NCI Common Terminology Criteria for Adverse Events) Version 4.0 for AE and SAE reporting.

### 12.4.1 Adverse Events (AE)

An adverse event is the appearance or worsening of any undesirable sign, symptom, or medical condition occurring after starting the study treatment even if the event is not considered to be related to study treatment. For the purposes of this study, the terms toxicity and adverse event are used interchangeably. Medical conditions/diseases present before starting study treatment are only considered adverse events if they worsen after starting study treatment. Abnormal laboratory values or test results constitute adverse events only if they induce clinical signs or symptoms, are considered clinically significant, or require therapy. Events that occur  $\leq 3$  months after radiation will be considered early toxicities while events occurring or persisting  $\geq 6$  months will be considered late toxicities.

Adverse events will be recorded after the start of radiation therapy. All events, even grade 1 will be recorded. AEs recorded until year 3.

Information about all adverse events, whether volunteered by the subject, discovered by investigator questioning, or detected through physical examination, laboratory test or other means, will be collected and recorded and followed as appropriate.

The occurrence of adverse events should be sought by non-directive questioning of the patient at each visit or phone contact during the study. Adverse events also may be detected when they are volunteered by the patient during or between visits or through physical examination, laboratory test, or other assessments. As far as possible, each adverse event should be evaluated to determine:

1. the severity grade based on CTCAE v.4 (grade 1-5)
2. its relationship to the study treatment (definite, probable, possible, unlikely, not related)
3. its duration (start and end dates or if continuing at final exam)

4. action taken (no action taken; study treatment dosage adjusted/temporarily interrupted; study treatment permanently discontinued due to this adverse event; concomitant medication taken; non-drug therapy given; hospitalization/prolonged hospitalization)
5. whether it constitutes an SAE

All adverse events will be treated appropriately. Such treatment may include changes in study treatment as listed in the dose modification section of this protocol (see section 6 for guidance). Once an adverse event is detected, it should be followed until its resolution, and assessment should be made at each visit (or more frequently, if necessary) of any changes in severity, the suspected relationship to the study treatment, the interventions required to treat it, and the outcome.

Information about common side effects already known about the treatment is discussed in section 2. This information will be included in the patient informed consent and will be discussed with the patient during the study as needed.

All adverse events will be immediately recorded in the patient research chart.

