was a secondary endpoint. Locoregional relapse was non-significantly different in the 3 arms at 10 years at 7.4%, 6.3% and 8.8%. Fourteen percent of patients received CMF chemotherapy. Running in parallel to STARTA, the UK STARTB trial was an accelerated hypofractionation trial comparing 50Gy in 2Gy daily fractions for 5 weeks versus 40Gy delivered in 2.67Gy daily for 15 days. This trial accrued 2215 stage I and II breast cancer patient between 1999 and 2001, treating patients with Cobalt-60, utilizing 2D planning. 23% of patients received chemotherapy +/- tamoxifen. In 1993, shortly after the RMH began their prospective trial, researchers with the National Cancer Institute of Canada (NCIC) and Ontario Clinical Oncology Group conducted a similar hypofractionated randomized trial comparing whole breast radiation of 50 Gy in 25 fractions versus a hypofractionated regimen 42.5 Gy in 16 fractions. 10 year data was published by Whelan et al in 2010 revealing equivalent outcomes in terms of cancer control and toxicity. Cosmesis was identical with excellent or good scores at 3 and 5 years in 77% of patients in both groups. Toxicities were comparable. Grade 2 and 3 toxicities were negligible. At 5 years, 87% of women in the experimental arm had no skin toxicity, and 66% of women had no subcutaneous toxicity, compared with 82% and 60% in the control arm, respectively. A major limitation of the Canadian study is the lack of a lumpectomy boost. The addition of an extra dose of radiation to the lumpectomy cavity, called a boost, has been shown in 2 randomized trials to significantly reduce further the risk of a local breast recurrence. Women in the NCIC study were not allowed a breast lumpectomy boost, but the UK start trials allowed an optional boost of 14Gy in 5 daily fractions. This occurred in 61% of patients in STARTA and 43% in STARTB. Adding a lumpectomy cavity boost in a sequential manner, adds an additional 5-8 treatment days of radiation, significantly increasing treatment burden. Several institutions have published results suggesting the safety of delivering the lumpectomy cavity boost concurrent with the whole breast radiation. From 2011-2015, the Radiation Therapy Oncology Group (RTOG) moved this single institution data into the phase III randomized trial 1005, randomizing women with a sequential vs. concurrent lumpectomy cavity boost. In this trial, the whole breast radiation could be administered in 15 vs. 25 fractions, at the discretion of the treating physician. In the concurrent arm, the breast received the UK START dose of 40Gy (2.66/day) while the lumpectomy cavity received an additional daily dose, resulting in a total of 48Gy delivered, 3.2Gy/day. In the conventional arm, the breast received the boost delivered over an additional 6-7 daily treatments as the treating physician discretion. The UK has tried to advance the hypofractionation concept further with the UK Fast trial. This trial enrolled 915 patients from 2004 to 2007 into one of three treatment arms: 50Gy in 25 fractions, 28.5Gy in 5 fractions or 30Gy in 5 fractions, all delivered over 5 weeks. The primary endpoint for the trial is change in photographic breast appearance. Initial publication in 2011, with a mean follow up of 3 years, has shown all arms acceptable in regards to conventional toxicity. The 50Gy and 28.5Gy arms appear to be similar in 2 year photographic appearance, however the 30Gy arms appears to be inferior with a risk ratio of mild to marked change in appearance 1.7:1 (1.26-2.29, p<0.001). There are two potential problems with this hypofractionation model. The radiobiology is not well understood when taking 6 days off between each treatment fractions, therefore the long term disease control outcomes will need to be carefully followed over the next 5-10 years

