## 2.5 Patient Satisfaction and Well-being as Patient Reported Outcomes (PROs)

The assessment of patient-reported outcomes (PROs) in clinical research provides important insight into how therapies impact the daily lives of patients. There is a growing recognition that patient-reported endpoints are critical in oncology trials, particularly when cosmesis and toxicity are likely to be different in the treatment arms. Patient-reported adverse event collection has been shown to be more thorough than collection by provider-report, with consistent underreporting of side effects by providers. Patient-reporting of health-related quality of life has become the gold standard in part because providers have been found to underestimate the pain and distress their patients are experiencing.

In a trial of different radiation schedules, in which cosmesis may be substantially different in the two arms of the study, patient-reported satisfaction and well-being are particularly important. Although short-term differences between the treatment arms may be momentarily relevant to patients, the long-term cosmetic outcomes are most critical, so we have chosen to collect this data at 24 months (and compare to historical controls). In order to avoid burdening patients, we will only administer the Breast-Q survey to patients at baseline, 6, and 24 months. The EQ-5D-3L will be administered at baseline and 2-8 weeks post radiation therapy.

We will be using the Breast Q survey tool to assess patient satisfaction and well-being. This tool has been validated for use in patients after breast conserving therapy to assess well-being and patient satisfaction with results, and is provided free of charge for academic research. Domains for the survey include: satisfaction with breast, adverse effects of

Protocol name: NOVEMBER (Novem- (9), BrEast Radiation), A Phase II trial of a 9 day course of whole breast radiotherapy for early stage breast cancer.

Version Date: 23NOV2021

Principal Investigator: [name]

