## 7 STUDY CALENDAR

Laboratory and clinical parameters during treatment are to be followed using individual institutional guidelines and the best clinical judgment of the responsible physician. It is expected that patients on this study will be cared for by physicians experienced in the treatment and supportive care of patients on this trial.

Tests & Observations	Prior to Registration	Before RT	Weekly during RT	2 to 8 weeks post RT	6 months post RT*	12 months post RT*	2 years post RT*	3 years post RT**	5 years Post RT**
Obtain Informed Consent 	X								
H&P	X 								
Symptom Directed Physical 			X	X	X	X	X	X	
ECOG Performance Score	X		X	X	X	X	X	X	
Recurrence Assessment 					X	X	X	X	X 
Adverse Events Assessment 			X	X	X	X	X	X	X 
Photographic Cosmetic Assessment 		X					X		
Serum or Urine HCG	X 								
Breast-Q Survey 		X			X		X		
Health Care Expense Diary			X 						
Health Care Expense Survey				X 					
EQ-5D Survey 		X		X					

\* +/- 6 weeks

\*\* +/- 3 months

1. Assessment of side effects related to radiation therapy should be assessed according to the history and physical examination.
2. For women of childbearing potential. Must be done within 7 days prior to registration.
3. All screening procedures should be performed within 28 days prior to registration except as otherwise noted.
4. Health Care Expense Diary should be provided to the patient each week during RT to assist in recall for the Health Care Expense Survey after radiation completion. (Appendix III)
5. Post hoc chart review only for 5 years.
6. Photographic assessment collection will be done as described in section 8.1.
7. Breast Q Survey should be completed by the patient prior to radiation therapy and at 6 months post radiation therapy. (Appendix I)
8. Health Care Expense Survey should be completed using the Health Care Expense Diary worksheet (Appendix III) during the 2-8 week window and is found in Appendix II.
9. EQ-5D Survey should be completed by the patient prior to radiation therapy and during the post radiation therapy 2-8 week window. (Appendix IV)
10. Disease recurrence will be determined by standard of care assessments as described in section 8.3.

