## **8.5 Safety**

Routine safety and tolerability will be evaluated from the results of reported signs and symptoms, scheduled physical examinations, vital sign measurements, and clinical laboratory test results. More frequent safety evaluations may be performed if clinically indicated or at the discretion of the investigator.

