## **8.6 Stopping Rules**

After 45 patients have been enrolled and followed for 6 months, an interim analysis will be performed of all patients with greater than 6 months of follow up. Based on an expected RT toxicity rate of  $\leq 10\%$ , if greater than 20% of our patients are found to have

Protocol name: NOVEMBER (Novem- (9), BrEast Radiation), A Phase II trial of a 9 day course of whole breast radiotherapy for early stage breast cancer.

Version Date: 23NOV2021

Principal Investigator: [name]

non-acute grade 2 or 3 RT toxicities  $\geq$  6 months after the completion of radiation, this study will be temporarily halted for interim review. Based on an anticipated recurrence rate of < 7%, if  $\geq$  15% of patients have a documented local recurrence, this study will be temporarily halted for interim review. Once temporarily halted, a team of experts will review the data to determine if it is safe to proceed with the trial or if the trial should be discontinued.

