## **14 APPENDICES**

Appendix I: Breast-Q Breast Conservation Module

# **NOVEMBER**

## **BREAST-Q™- BREAST CONSERVING THERAPY MODULE (POSTOPERATIVE) 2.0**

**Patient Study ID:** 103976-01-\_\_\_\_\_

**Patient Initials:** \_\_\_\_\_

**Date of Completion:** \_\_\_\_\_ / \_\_\_\_\_ / \_\_\_\_\_

All applicable Breast Conserving modules should be completed at the indicated time points in the study calendar.

- Satisfaction with Breasts
- Adverse Effects of Radiation (to be completed post radiation only)
- Psychosocial Well-Being
- Physical Well-Being: Chest
- Sexual Well-Being

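### Late toxicity and the 20% halt trigger rest on open questioning and symptom-directed examination, with no named late effect required to be graded, so the trigger is exposed to downward bias of unknown size

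*Combined protocol and SAP*

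**What the plan says.** Section 12.4.1 (Adverse Events) sets out how events are to be looked for: "The occurrence of adverse events should be sought by non-directive questioning of the patient at each visit or phone contact during the study". The same section casts the recording net wider: "Information about all adverse events, whether volunteered by the subject, discovered by investigator questioning, or detected through physical examination, laboratory test or other means" is to be collected, and grade 1 events count. A note to the study calendar (section 7) adds: "Assessment of side effects related to radiation therapy should be assessed according to the history and physical examination". Section 8.5 names as safety sources "reported signs and symptoms, scheduled physical examinations, vital sign measurements, and clinical laboratory test results". In the calendar, the examination at each post-radiation clinic visit up to 3 years is a symptom-directed physical. There is no separate row for vital signs, and the only laboratory row is the pregnancy test.

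Section 2.5, in arguing for patient-reported outcomes, says: "Patient-reported adverse event collection has been shown to be more thorough than collection by provider-report, with consistent underreporting of side effects by providers". Appendix I contains a prompted Breast-Q page on adverse effects of radiation, and section 2.5 schedules Breast-Q at baseline, 6 and 24 months. That page is not among the domains listed for analysis in 9.2.1, and neither 8.6 nor 9.2.2 mentions it.

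The halt rule in 8.6 reads: "Based on an expected RT toxicity rate of $\leq 10\%$ , if greater than 20% of our patients are found to have" non-acute grade 2 or 3 radiation toxicity at 6 months or later, the trial pauses for review. The look takes place once 45 patients have been followed for 6 months. The underlying expectation, in 2.2, is 7-10% for grade 2 or greater non-acute toxicity, and it is expressly non-cosmetic.

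**The concern.** Section 2.2 names the effects that matter after breast radiation: rib fracture, lung fibrosis, ischemic heart disease, edema, telangiectasia, shrinkage and induration. That list is never turned into an assessment. What gets graded depends on what the patient brings up, and on an examination whose scope follows her symptoms in part. Several of the named effects would not be evident on a breast examination.

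Section 8.6 holds the only numeric late-toxicity rule. The DSMC's listing of grade 3 or greater toxicities in 12.3 covers treatment and a 30-day window, so late grade 2 events fall outside it. Because the 20% threshold is a fixed number, each affected patient who goes unrecorded makes a halt less likely. In a trial that section 5.3.2 describes as being about toxicity and cosmesis, a low late-toxicity rate should reflect the schedule and not the way the question was put.

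**Working it through.** **The plan's own figure.** The plan gives no operating characteristics for the 8.6 trigger, so there is none to reproduce. The calculation below does not use the primary sample size.

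**Inputs from the documents.** Interim n = 45 (8.6); threshold more than 20% (8.6); expected rate 10% or less (8.6), 7-10% (2.2).

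**Input that is assumed.** Capture s is the share of truly affected patients whose event is recorded. The documents give no value. The range used is 100% down to 70%, with each affected patient equally likely to be captured and no false positives.

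**Step 1, the cut-off.** 0.20 × 45 = 9. More than 20% therefore means at least 10 of 45.

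**Step 2, the recorded rate.** Recorded rate = true rate × s. For a true 20%, this is 20%, 18%, 16% and 14% at s = 100%, 90%, 80% and 70%.

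**Step 3, the chance of a halt.** P(X ≥ 10) with X ~ Binomial(45, true rate × s):

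| True rate | s = 100% | s = 90% | s = 80% | s = 70% |
|---|---|---|---|---|
| 10% | 1.2% | 0.6% | 0.3% | 0.1% |
| 20% | 41% | 28% | 17% | 9% |
| 25% | 72% | 58% | 41% | 25% |
| 30% | 91% | 81% | 67% | 48% |

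**Step 4, the effective threshold.** The true rate at which the expected recorded rate reaches 20% is 0.20 / s: 20%, 22.2%, 25% and 28.6%.

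**Sensitivity to n.** Section 8.6 takes in all patients with more than 6 months of follow-up, so n may exceed 45. With n = 60 the cut-off is 13 (0.20 × 60 = 12), and the row for a true 20% becomes 42%, 28%, 15% and 7%. The pattern is the same.

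**The case against.** The strongest reply is that 12.4.1 does not rely on the open question alone. Investigator questioning, examination and tests also feed the record, the calendar has an adverse event assessment at every post-radiation time point, and edema, telangiectasia, shrinkage and induration are signs a clinician can see or feel. This stands. A reader might infer that an effect the patient does not mention is recorded as absent; the documents do not support that. What remains is that no named effect must be graded.

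A reader might also see a contradiction between 2.5 and 12.4.1. There is none. Section 2.5 compares patient with provider report, not open with prompted questions, and the protocol acts on it by using Breast-Q, including a chest page that asks about pain and arm swelling. Its bearing is narrower: it recognises a weakness in the source on which 8.6 and 9.2.2 depend.

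A third tempting reading is that the trial measures toxicity less completely than the studies it is judged against, since section 2.1 reports of the Canadian trial: "At 5 years, 87% of women in the experimental arm had no skin toxicity, and 66% of women had no subcutaneous toxicity". That suggests patient-by-patient grading but does not prove it, and it concerns any toxicity at 5 years, not the non-cosmetic grade 2 or greater rate. Section 9.2.2 also plans a Fisher's exact test against database patients, whose toxicity collection is not described. The direction of any relative bias is unknown.

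Three further points have weight. At a true 20% rate with complete capture the trigger is still missed 59% of the time, which comes from n = 45 and the cut-off. The rule is a pause for review, alongside quarterly DSMC review. And the CRFs (section 11) are separate documents that may already list named effects; if so, the protocol should say so.

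**Conclusion.** The point holds as an exposure, not as a demonstrated bias. The protocol requires no structured grading of late effects, and its prompted patient-reported radiation page has no stated part in adverse event grading, in 8.6 or in 9.2.2. Against a fixed threshold, under-recording can only lower the chance of a halt. How much is not derivable: the drop from 41% to 28%, 17% or 9% at a true 20% rate is an illustration that rests entirely on the assumed capture rates.

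A reader might go further and conclude that the reported late-toxicity rate will be biased towards looking safe. The documents show neither that under-recording will occur in this trial nor how toxicity was collected in the earlier trials or the database, so that conclusion is not supported. The photographic primary endpoint is not affected. The change is worth making because it is cheap and because late effects at 6 to 36 months cannot be reliably reconstructed afterwards.

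**What to change.** In 12.4.1, keep non-directive questioning for unexpected events and add, in substance:

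> At each scheduled post-radiation adverse event assessment the clinician grades a fixed CTCAE 4.0 list from grade 0 upward: rib fracture, lung fibrosis, ischemic heart disease, breast edema, telangiectasia, breast shrinkage, breast induration, pain and arm lymphedema. At 6 and 24 months the completed Breast-Q page on adverse effects of radiation is available to the clinician before grading.

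Use these grades for the 9.2.2 incidence and for 8.6. In 8.6, state which listed effects are cosmetic and count only non-cosmetic effects of grade 2 or higher, so that the trigger matches the 7-10% expectation in 2.2. This matters because 2.2 reports shrinkage in 26% and induration in 14% of the UK trial arm, without grades; counting such effects would set the trigger against an expectation that never included them.

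Cost: one extra CRF page at five visits already in the calendar (2-8 weeks, 6 and 12 months, 2 and 3 years). The recorded rate will be somewhat higher. False alarms are a small worry: at a fully captured 10% rate the chance of a halt is 1.2%. Grading the trial patients from a list could also tilt the Fisher comparison against them, so that result must carry the caveat that toxicity may have been collected differently in the database patients.
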